8.3 Documentation of AEs

The AE will be described in the source documents (e.g., electronic or paper diary card) and captured on the CRF and will include:

- A description of the AE
- The onset date, duration, date of resolution
- Severity (mild, moderate, or severe– what is the impact on the participant's daily life?)
- Seriousness (i.e., is it an SAE?)
- Any action taken, (e.g., treatment, follow-up tests)
- The outcome (recovery, death, continuing, worsening)
- The likelihood of the relationship of the AE to the trial treatment (Unrelated, Possible, Probable, Definite)

Changes in the severity of an AE will be reported. AEs characterised as intermittent will be documented for each episode. All AEs will be followed to adequate resolution, where possible.

8.4 Assessing the relatedness (causality) of a participant's AE

The relationship of the event to the trial intervention will be graded/ assessed as follows:

Unrelated	Unlikely temporal relationship to study product. Alternate aetiology likely (clinical state, environmental or other interventions) and does not follow known typical or plausible pattern of response to study product
Possible	Reasonable temporal relationship to study product; or event not readily produced by clinical state, environmental or other interventions; or similar pattern of response to that seen with other vaccines
Probable	Reasonable temporal relationship to study product; and event not readily produced by clinical state, environment, or other interventions or known pattern of response seen with other vaccines
Definite	Reasonable temporal relationship to study product; and event not readily produced by clinical state, environment, or other interventions; and known pattern of response seen with other vaccines

8.5 Assessing the expectedness of a participant's AE

The severity of an Adverse Events will be graded/ assessed as follows:

Grade 0	None
Grade 1	Mild: Transient or mild discomfort (< 48 hours); No interference with activity; No medical intervention/therapy required
Grade 2	Moderate: Mild to moderate limitation in activity – some assistance may be needed; no or minimal medical intervention/therapy required
Grade 3	Severe: Marked limitation in activity, some assistance usually required; medical intervention/therapy required.
Grade 4	Potentially Life-threatening: Requires assessment in A&E or hospitalisation

8.6 Reporting of safety events

Sponsor-Investigator Reporting Procedures

The Sponsor-Investigator must assess and categorise the Expedited Safety Reports received from Investigators and report these to all Site Principal Investigators, the approving HREC and TGA in accordance with the NHMRC's 'Safety monitoring and reporting in clinical trials involving therapeutic goods' (November 2016) and any additional requirements of the approving HREC. All safety reports must clarify the impact of the safety event on participant safety, trial conduct and trial documentation.

The Sponsor-Investigator is responsible for the following reporting to PIs, the HREC(s) and TGA:

1. All SSIs that meet the definition of a USM within 72 hours of becoming aware of the issue.
2. All other SSIs within 15 calendar days of instigating or becoming aware of the issue
3. For SSIs leading to an amendment of trial documentation:
 - a. Submit details of the SSI without undue delay and no later than 15 calendar days of becoming aware of the issue.
 - b. Submit amendment to the HREC without undue delay.
4. For SSIs leading to temporary halt or early termination of a trial for safety reasons:

- a. Communicate reasons, scope of halt, measures taken, further actions planned without undue delay and no later than 15 calendar days of decision to halt.
- b. For a temporary halt, notify the PIs, HREC and TGA when the trial restarts, including evidence that it is safe to do so.

The Sponsor will also report SUSARs to the TGA as follows:

1. Fatal or life-threatening SUSARs immediately, but no later than 7 calendar days after being made aware of the issue (follow up info within a further 8 calendar days)
2. All other SUSARs no later than 15 calendar days of being made aware of the issue

The Sponsor is responsible for providing the additional safety information to the approving HREC:

1. Provide an annual safety report, including a summary of the evolving safety profile of the trial

The Sponsor is also responsible for providing any updated Product Information/Investigator's Brochure to Investigators.

9 DATA AND INFORMATION MANAGEMENT

The Principal Investigator is responsible for storing essential study documents relevant to data management and maintaining a site-specific record of the location(s) of the site's data management-related Essential Documents.

The Principal Investigator is responsible for maintaining adequate and accurate source documents that include all key observations on all participants at their site. Source data will be attributable, legible (including any changes or corrections), contemporaneous, original, accurate, complete, consistent, enduring, and available. Changes to source data collected by MCRI must be traceable and explained in a note at relevant variables on the electronic case report form (eCRF). A site-specific Source Document Plan will be maintained to indicate the location(s) of source documents.

The Principal Investigator will maintain accurate data collection forms (known as case report forms - CRFs) and ensure that the collected and reported data is accurate, legible, complete, entered promptly, and enduring.

Any person delegated to collect data, perform data entry, or sign for data completeness will be recorded on the delegation log and trained to perform these study-related duties and functions.

Data generated for this study will be handled according to the relevant standard operating procedures (SOPs) and Data Management Plan (DMP). Full details of all processes are provided in a separate study-level DMP.

9.1 Data management

9.1.1 Data generation (source data)

Source documents are all documents used by the investigator that relate to the participant's medical history, that verify the existence of the participant, the inclusion and exclusion criteria, and all records covering the participant's participation in the study. They include but are not limited to

laboratory reports, memoranda, vaccination records, hospital records, and participant files. The site principal investigator is responsible for maintaining source documents.

An electronic CRF (eCRF) will be completed for all recruited participants.

In this study, the following types of data will be collected:

- Identifying personal information (contact details, dates of birth, home address and telephone contact and gender)
- Sensitive information, including health data (dates of COVID-19 vaccinations, medical history, primary COVID vaccine (Pfizer-BioNTech (BNT162b2, or *Comirnaty*®), AstraZeneca (ChAdOx1-S, or *Vaxzevria*®)); intervention vaccine (Pfizer-BioNTech (NT162b2, or *Comirnaty*®), Moderna (mRNA-1273, or *Spikevax*®))
- Reactogenicity information (pain, tenderness, erythema/redness, induration/swelling, fever, nausea/vomiting, headache, fatigue/malaise, myalgia, arthralgia)
- Adverse events and serious adverse events
- Biological information (blood sample, immunologic assay results, including binding antibodies, functional antibodies, neutralizing antibodies, cellular immunity)

Source Document Plan

The source documents for this study include: COVID-19 vaccination details, date of birth, and sex); questionnaires completed by the participant and researcher (MCRI's eCRF).

A Source Document Plan will be maintained to document the source (i.e., original recording) for each data discrete item/category of items collected for the study. This Source Document Plan, signed and dated by the Principal Investigator, will be prepared before recruitment of the first participant and filed in the site's Investigator Site File.

9.1.2 Data capture methods and data use, storage, access, and disclosure during the trial

Data collection methods

Data capture and entry will be electronic. Data for this study will be collected and entered using electronic data collection forms, completed by authorised study staff and participants where applicable.

The following licensed research data collection tools will be used:

- Study data will be collected and managed using REDCap electronic data capture tools, hosted at MCRI. REDCap (Research Electronic Data Capture) is a secure, web-based software platform designed to support capture for research studies, providing 1) an intuitive interface for validated data capture; 2) audit trails for tracking data manipulation and export procedures; 3) automated export procedures for data downloads to common statistical packages; and 4) procedures for data integration and interoperability with external sources. (12, 13)

- Data recorded will be linked by unique participant identifiers

Further details on the data variables are in the study DMP.

Use of the data

The data will be used for the analyses specified in the protocol and Statistical Analysis Plan (SAP).

Following the completion and analysis of the study, the data will be retained long-term following the mandatory archive period for use in future research projects.

Storage and access

Electronic data will be securely stored in MCRI's REDCap database system and in files stored in MCRI's network file servers, which are backed up nightly. Files containing private or confidential data will be stored only in locations accessible by appropriate designated members of the research team.

REDCap is hosted on MCRI infrastructure and is subject to the same security and backup regimen as other systems (e.g., the network file servers). Data is backed up nightly to a local backup server, with a monthly backup taken to tape and stored offsite. REDCap maintains an audit trail of data creation, update, and deletion events accessible to project users who are granted permission to view it. Access to REDCap will be provided via a REDCap user account created by the MCRI system administrator. The permissions granted to each user within each REDCap project will be controlled by and will be the responsibility of the study team delegated this task by the Principal Investigator. REDCap has functionality that makes adding and removing users and managing user permissions straightforward. All data transmissions between users and the REDCap server are encrypted. The instructions for data entry to REDCap must be read and the training log signed before personnel commencing data entry on REDCap.

Authorised representatives of the sponsoring institution and representatives from the HREC, Research Governance Office, and regulatory agencies may inspect all documents and records required to be maintained by the Investigator for the participants in this study. The study site will permit access to such records.

Disclosure

The study protocol, documentation, data, and all other information generated will be held in strict confidence. No information concerning the study, or the data will be released to any unauthorised third party without the prior written approval of the sponsoring institution. Clinical information will not be released without the participant's written permission, except as necessary for monitoring by the HREC, Research Governance Office, or regulatory agencies.

9.1.3 Data confidentiality

Participant confidentiality is strictly held in trust by the Principal Investigator, participating investigators, research staff, and the sponsoring institution and their agents. This confidentiality is extended to cover the testing of biological samples and genetic tests in addition to the clinical information relating to participating participants.

To preserve confidentiality and reduce the risk of identification during collection, analysis, and storage of data and information, the following will be undertaken:

- (1) The number of private/confidential variables collected for individual study participants has been minimised. The data collected will be limited to that required to address the primary and secondary objectives.

- (2) Participant identifiers will be stored separately from the data collected, and documents with identifiers will be stored separately from participant data. Participant data and samples will be identified using a unique participant study number assigned to the study participant (“re-identifiable”). The Principal Investigator is responsible for storing a master file of names and other identifiable data with the participant ID; access to this document will be restricted to the site study team. The master file will be stored securely and separately from study data in locked/ password-protected databases with passwords kept separately. Age and sex will be included in the data; however, it is unlikely to make specific participants or families identifiable as identifiers will be stored separately.

Separation of the roles responsible for the management of identifiers and those responsible for analysis of content. The Principal Investigator will ensure access to the data is restricted, using REDCap’s permission control functionality (“REDCap Users and Permissions”).

9.1.4 Quality assurance

Data validity and quality assurance will be ensured by the following:

- (1) Data collection and entry into the eCRF will be completed by authorised staff designated by the investigator. Appropriate training on eCRF completion will be conducted with the relevant investigator and all authorised staff before the study starts and any data is entered.

- (2) All data will be entered in English. eCRFs are to be completed as soon as possible after each participant’s visit. For information collected specifically for the study, data may be entered directly to the eCRF without duplicating the information across separate source documentation and eCRF. If data are unavailable or missing, this will be indicated on the eCRF. Changes or corrections made on eCRF will be tracked via an audit trail.

- (3) Once the eCRFs have been entered, edit and consistency checks will be performed as outlined in the DMP. Data queries generated for logic and legality will be reviewed by authorised study staff for clarification. After resolving the queries, the responsible Data Manager will make the necessary updates to the database. An audit trail of all changes to the database will be maintained. Once all queries have been resolved, the database will be locked.

- (4) The Principal Investigator will be required to sign off on the eCRF data before the final database lock.

- (5) An audit is a systematic and independent examination of trial-related activities and documents to determine whether the evaluated related activities were conducted. The data were

recorded, analysed, and accurately reported according to the protocol, study SOPs, GCP, and the applicable regulatory requirement(s).

Authorised representatives of MCRI, its designee, a regulatory authority, or the IEC may visit the centre to perform audits or inspections. The investigator should contact MCRI or designee immediately if a regulatory agency contacts them about an inspection at their centre. If an audit or inspection occurs, the site PI agrees to allow the auditor/inspector direct access to all relevant documents and allocate their staff's time to the auditor/inspector to discuss findings and any relevant issues.

The statistician will be provided with anonymised data, with participants identifiable only by unique participant study number/code. The statistician will analyse the de-identified data.

9.1.5 Archiving - Data and document retention

Archiving

The Investigator will take measures to prevent accidental or premature destruction of these documents. For this study, essential documents, and data (including biological samples) will be retained for a minimum of 7 (seven) years post-study.

The central study site and laboratory for this study are:

- New Vaccines Research Group, Infection & Immunity, Murdoch Children's Research Institute

Records will not be destroyed without the written consent of the Principal Investigator.

Destruction

After the archival period of 7 (seven) years, The Principal Investigator will take measures to ensure secure destruction of hardcopies of study data. Any hardcopy data will be disposed of via a confidential shredding process. Noting that simply deleting files does not destroy the information, electronic CRFs will be destroyed under guidance from MCRI IT to ensure the files are permanently deleted.

The electronic, anonymised database will not be destroyed

At the end of the archival period, eCRFs will be disposed of via secure destruction methods. Electronic databases will be retained by MCRI, stored on the secure server

9.1.6 Sample management: collection and storage

The study has been discussed with the biobanking team and a Biobanking Request Form has been submitted.

10 TRIAL OVERSIGHT

10.1 Governance structure

The Governance structure is outlined below.

10.1.1 Trial Management Group (TMG)

The Site Principal Investigator is responsible for supervising any individual or party to whom they have delegated tasks at the trial site. They must provide continuous supervision and documentation of their oversight. To meet this GCP requirement, a small group will be responsible for the day-to-day management of the trial and will include at a minimum the Site PI, project manager, data manager and

a representative from the Immunology team. The group will closely review all aspects of the conduct and progress of the trial, ensuring that there is a forum for identifying and addressing issues. Meetings must have minutes with attendees listed, pertinent emails retained, and phone calls documented.

10.1.2 Trial Steering Committee (TSC)

A TSC will be established to provide expert advice and overall supervision and ensure that the trial is conducted to the required standards. The TSC will meet at least annually, with more frequent meetings as needed, and will work to a Terms of Reference.

10.1.3 Safety Monitoring

Monitoring will be performed according to Good Clinical Practice (GCP) guidelines by external monitors. Following written SOPs, the monitors will verify that the clinical trial is conducted, and data are generated, documented and reported in compliance with the protocol, GCP and the applicable regulatory requirements. The investigator will provide direct access to all trial related source data/documents and reports for the purpose of monitoring.

Independent Safety Monitor

An Independent Safety Monitor will be responsible for providing independent safety monitoring in a timely fashion. The Independent Safety Monitor will operate within agreed terms of reference and will provide input to the trial investigators.

Independent Data Safety Monitoring Board (DSMB)

Safety oversight will be under the direction of a DSMB. The DSMB will meet at least 6 monthly to review SAEs or AEs deemed possibly, probably or definitively related to study interventions. The DSMB will make recommendations concerning the conduct, continuation or modification of the study for safety reasons. The DSMB will meet virtually prior to the commencement of the trial then again on at least 2 occasions to review the one-month immunogenicity data for the standard and fractional-dose recipients, and to review the 6 months data. The DSMB will decide whether a fourth dose is required, based on up-to-date safety data, for participants who received a fractional dose and did not mount an adequate antibody response. The DSMB will operate under the rules of an approved charter that will be written and reviewed at the organisational meeting of the DSMB. The DSMB will be chaired by an experienced vaccine trial specialist and will contain one statistician, one adult physician and representatives from Indonesia and Mongolia. Members of the DSMB will be independent of trial conduct.

10.2 Site Monitoring

Trial site monitoring is conducted to ensure that the rights and well-being of trial participants are protected, that the reported trial data are accurate, complete, and verifiable, and that the conduct of the trial is in compliance with the currently approved protocol and amendment(s), good clinical practice and applicable regulatory requirements.

Full details of trial site monitoring are documented in the Clinical Monitoring Plan (CMP). The CMP describes in detail who will conduct the monitoring, at what frequency monitoring will be done, at what level of detail monitoring will be performed, and the distribution of monitoring reports.

Monitoring for this trial will be performed by one of the three trial managers. The monitoring will take place on-site. The monitors will review 100% of original signed consent forms, trial eligibility data and data related to primary outcome, safety and other key data variables; review of all withdrawals from trial; targeted review of other data including investigational vaccine administration and accountability.

The investigational site will provide direct access to all trial related sites, source data/documents, and reports for the purpose of monitoring and auditing by the sponsor, and inspection by local and regulatory authorities.

10.3 Quality Control and Quality Assurance

Both the Sponsor-Investigator and Site Investigator have responsibilities in relation to quality management.

The Sponsor-Investigator will develop SOPs that identify, evaluate and control risk for all aspects of the trial, e.g., data management, training, eligibility, informed consent and adverse event reporting. The Sponsor-Investigator will also implement quality control (QC) procedures, which will include the data entry system and data QC checks. Any missing data or data anomalies will be communicated to the study staff for clarification/resolution.

As outlined in the previous section (Site Monitoring), the trial monitors will verify that the clinical trial is conducted and data are generated and biological specimens are collected, documented (recorded), and reported in compliance with the protocol, good clinical practice and applicable regulatory requirements.

In the event of non-compliance that significantly affects human participant protection or reliability of results, the Sponsor-Investigator will perform a root cause analysis and corrective and preventative action plan (CAPA).

In addition, the clinical site will perform internal quality management of trial conduct, data and biological specimen collection, documentation and completion.

11 STATISTICAL METHODS

11.1 Sample Size Estimation

Sample size calculations were performed using nQuery 8 software. Precision-based sample size calculations were performed based on the reactogenicity outcomes. Assuming the percentage of participants reporting local or systemic reactions is 50%, 100 participants will produce a confidence interval that is 9.8 percentage points from the observed percentage. For immunogenicity, sample size calculations were based on the comparison of seroresponse rates between the standard and fractional dose groups within the non-inferiority framework. Assuming a -10% non-inferiority margin and a seroresponse rate of 95% in both groups, the study will have 90% power for the non-inferiority comparisons using 100 participants per group. If we make the more conservative assumption that the seroresponse rate is lower in the fractional-dose group (93% versus 95% seroresponse), then 100 per group will provide 66% power.

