7.2.10 Replacements

Participants who have been randomised and enrolled may NOT be replaced.

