11.3 Methods of analysis

Reactogenicity following immunisations will be presented as the number and percentage of participants self-reporting local reactions (pain; tenderness, redness; swelling at or near the injection site) and systemic reactions (fever, nausea/vomiting, headache, fatigue/malaise, myalgia), and the severity of

these reactions (mild, moderate, severe, life-threatening or fatal). Reactogenicity data will be presented separately by group and time point.

For immunogenicity, antibody levels will be presented as geometric mean titres (GMT) with 95% confidence intervals. Changes from baseline will be expressed as geometric mean fold ratios (GMFR), calculated as the ratio of the post-booster GMT to the baseline GMT. Seroresponse will be defined as a ≥ 4 -fold rise in post-booster antibody levels compared to baseline (or ≥ 2 -fold rise if the baseline (pre-booster) antibody level was ≥ 200 BAU/ml). To assess the non-inferiority of the fractional dose compared with the standard dose, comparisons will be based on the difference in percentage of participants with seroresponse. Using a non-inferiority margin of -10% (fractional-dose minus standard dose), non-inferiority will be declared if the lower limit of the 95% confidence interval around the difference in percentages is greater than -10%, where confidence intervals are calculated using Score-based methods (14)

Analyses will be performed using Stata software (15). Detailed methodology will be outlined in a separate Statistical Analysis Plan.

Primary outcome (All samples at all timepoints)

The binding IgG data using the Euroimmun S1 IgG ELISA kits will be reported as relative units/ml (RU/ml) as per manufacturer's instructions. A result of < 8 RU/ml: negative (IgG Antibodies for SARS-CoV-2 are not detected), ≥ 8 to < 11 RU/ml: borderline (IgG antibodies is indeterminate/equivocal with this sample), ≥ 11 RU/ml: positive (IgG antibodies for SARS-CoV-2 are detected). Conversion to binding antibody units (BAU/ml) will also be done using the WHO reference serum from NIBSC, UK. Data will be presented as geometric mean titres and 95% confidence intervals.

Analysis comparing fractional and standard dose groups will be based on seroresponse rate (SRR) at 28 days post study vaccine, defined as:

- ≥ 4 -fold rise in GMCs at 28 days post study vaccine from baseline among subjects with no pre-dose (< 200 BAU/ml) detectable titres

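### The stated 90% and 66% non-inferiority power match a Wald formula; the score-based interval in Section 11.3 gives about 83% and 58% at 100 per group, before any missing data

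*Combined protocol and SAP*

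**What the plan says.** Section 11.1 bases the immunogenicity sample size on non-inferiority of the seroresponse rate. The base case is "Assuming a -10% non-inferiority margin and a seroresponse rate of 95% in both groups", for which "the study will have 90% power for the non-inferiority comparisons using 100 participants per group". A second case lowers the fractional-dose rate to 93% against 95%; "then 100 per group will provide 66% power". The software is given as nQuery 8, without the test or formula chosen.

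Section 11.3 sets the decision rule: "non-inferiority will be declared if the lower limit of the 95% confidence interval around the difference in percentages is greater than -10" percent, "where confidence intervals are calculated using Score-based methods (14"). Reference 14 is a published comparison of eleven interval methods for the difference between two independent proportions. No variant is named, and detailed methods are left to a separate SAP.

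Section 11.1 counts all 100 participants per group. Section 7.2.10 states: "Participants who have been randomised and enrolled may NOT be replaced". Section 11.2 recognises that people who withdraw may not contribute blood samples at every time point.

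**The concern.** Power is a property of the test that will be run. Section 11.1 appears to use one interval for planning while Section 11.3 uses another for the decision. At response rates near 95% the two differ materially. The score interval is asymmetric and its lower limit lies further from the estimate than the Wald limit does, so fewer outcomes count as non-inferior.

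This comparison is the main immunogenicity result of the trial. Under Section 11.4, a conclusion that fractional doses are inadequate would be made public and shared with WHO. Anyone interpreting a comparison that misses the margin needs to know how often that would happen if the doses were truly equivalent. The protocol implies 10%. The planned analysis gives about 17%, and in the protocol's own more conservative scenario about 42% instead of 34%.

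**Working it through.** **Inputs.** Margin 0.10; rates 95% vs 95% and 93% (fractional) vs 95% (standard); n = 100 per group (Section 11.1). Decision on the lower limit of a two-sided 95% interval, so one-sided 0.025 and z = 1.96 (Section 11.3). Allocation is equal (Section 6).

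**Step 1: reproduce the stated figures.** Unpooled normal approximation, with pS the standard-dose and pF the fractional-dose rate:

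power = Φ( [0.10 − (pS − pF)] / SE − 1.96 ), where SE = √[ pS(1 − pS)/n + pF(1 − pF)/n ].

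- 95 vs 95: SE = √(2 × 0.95 × 0.05/100) = 0.0308; power = Φ(0.10/0.0308 − 1.96) = 90.05%.
- 93 vs 95: SE = √(0.93 × 0.07/100 + 0.95 × 0.05/100) = 0.03356; power = Φ(0.08/0.03356 − 1.96) = 66.4%.

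Both match. Three alternatives match neither figure: one-sided 0.05 (94.5%, 77.0%), the same formula with a continuity correction (83.1%, 55.0%), and the asymptotic Farrington-Manning formula (80.3%, 55.8%).

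**Step 2: see how the two intervals differ.** The Newcombe lower limit is d − √[ (pF − lF)² + (uS − pS)² ], where d = pF − pS, and lF and uS are the Wilson lower and upper limits of the two observed proportions. Take 95/100 responders on standard dose and 92/100 on fractional dose, so d = −0.03:

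- Wald: SE = √(0.92 × 0.08/100 + 0.95 × 0.05/100) = 0.0348; lower limit = −0.03 − 1.96 × 0.0348 = −9.8%. Passes.
- Newcombe: lF = 0.850, uS = 0.978; lower limit = −0.03 − √(0.070² + 0.028²) = −10.6%. Fails.

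The score interval needs at least 93/100 where Wald accepts 92/100.

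**Step 3: exact power under the Section 11.3 rule.** Sum Bin(x; 100, pF) × Bin(y; 100, pS) over all tables (x, y) whose lower limit exceeds −0.10.

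| Method, n = 100 per group | 95 vs 95 | 93 vs 95 |
|---|---|---|
| Stated in Section 11.1 | 90% | 66% |
| Wald interval, exact | 88.6% | 66.5% |
| Newcombe hybrid score | 83.2% | 58.0% |
| Miettinen-Nurminen | 83.2% | 58.0% |
| Farrington-Manning | 83.2% | 58.0% |
| Newcombe, continuity-corrected | 76.6% | 49.6% |

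A simulation of 200,000 trials with the Newcombe interval gave 83.2% and 57.9%.

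**Step 4: missing Day 28 samples.** The documents give no rate, so 5% and 10% are assumptions. Newcombe interval, exact:

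| Evaluable per group | 95 vs 95 | 93 vs 95 |
|---|---|---|
| 95 (5% missing) | 81.4% | 56.2% |
| 90 (10% missing) | 79.4% | 54.1% |

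**Step 5: context.** Power of 90% at 95 vs 95 would need about 120 to 125 evaluable per group (Newcombe 90.1% at 120; Miettinen-Nurminen 90.7% at 125). All figures are per comparison. There are four fractional-versus-standard comparisons (two priming vaccines by two boosters) in separate participants. If all four are truly 95 vs 95, the chance that every one succeeds is 0.832⁴ = 48%, against 0.90⁴ = 66% on the stated power.

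**The case against.** The strongest defence is that nothing was miscalculated. Section 11.1 is correct for a standard planning formula, and planning approximations often differ from the final analysis. That is true: the error is a mismatch between planning and analysis methods. It still leaves the protocol claiming a power that its chosen test does not have.

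Other points stand in part:

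- The Wald origin is inferred because both figures match. The protocol names only the software.
- The score variant is unnamed, so 83% and 58% apply to the uncorrected intervals and the full range is 77–83% and 50–58%. No score variant examined reaches 90% or 66%.
- In the base case about 1.4 points of the gap (90.05% to 88.6%) is error in the normal approximation; the remaining 5.4 (88.6% to 83.2%) come from the interval. In the 93 vs 95 case the gap is all due to the interval.
- Section 11.2 covers visits to 12 months, whereas this endpoint is at Day 28. Early losses may be few, and at 5% missing they cost less than 2 points.
- The protocol does not require all four comparisons to succeed. The 48% figure only shows why the power should be labelled as per comparison.
- The decision rule remains valid. At the margin (85% vs 95%) the exact one-sided error is 2.3% for the score interval and 3.4% for Wald. The score interval is the better choice, and the power statement is what should change.

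**Conclusion.** The concern holds. With 100 evaluable per group and the planned score-based interval, power per comparison is about 83% at 95 vs 95 and about 58% at 93 vs 95. The stated 90% and 66% are therefore about 7 and 8 points too high. This assumes an uncorrected score interval; with a continuity correction the shortfall is about 13 and 16 points. It uses the protocol's own response rates and margin, and takes no account of missing samples, which can only lower power further. The validity of the analysis and its type I error are not affected.

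**What to change.** In Section 11.3 (and the separate SAP), name the score variant and say whether a continuity correction is used. In Section 11.1, replace the two power figures with values calculated for that interval. For the uncorrected Newcombe interval, suitable text would be:

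> With 100 evaluable participants per group, exact power for each fractional-versus-standard comparison, based on the two-sided 95% Newcombe hybrid score interval without continuity correction, is 83% if seroresponse is 95% in both groups and 58% if it is 93% (fractional) and 95% (standard). If 5% of Day 28 results are missing, power is 81% and 56%; if 10% are missing, 79% and 54%.

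If the continuity-corrected version is intended, the figures at 100 per group are 77% and 50%. Keep the score interval: moving to Wald to preserve the stated figures would raise the error rate at the margin to 3.4% and still give only 88.6% exact power in the base case.

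The cost is wording only, with a less favourable power statement. Enrolment, margin and decision rule stay as they are.
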